3.1.1 Hypotheses

The study will evaluate whether the single-incision sling treatment (Solyx) is non-inferior to the outside-in transobturator (Obtryx) treatment. The null and alternative hypotheses for this evaluation are

$$H_0: \pi_{treatment} - \pi_{control} \leq -\Delta$$

$$H_a: \pi_{treatment} - \pi_{control} > -\Delta$$

where $\pi_{treatment}$ and $\pi_{control}$ are the proportions of subjects with treatment success in the treatment and control groups, respectively, and Δ is the non-inferiority margin.

3.1.3 Statistical Methods

Non-inferiority will be evaluated using a two-sided 90% confidence interval for the treatment difference (single-incision minus transobturator). If the entire confidence interval is above -15%, non-inferiority will be demonstrated. The confidence interval will be calculated based on the pooling of treatment differences across propensity score strata for a binary endpoint, as described in Section 4.3.

[REDACTED]

[REDACTED]

[REDACTED]

[REDACTED]

[REDACTED]

[REDACTED]

[REDACTED]

[REDACTED]

[REDACTED]

[REDACTED]

[REDACTED]

[REDACTED]

[REDACTED]

[REDACTED]

[REDACTED]

[REDACTED]

[REDACTED]

[REDACTED]

[REDACTED]

[REDACTED]

[REDACTED]

[REDACTED]

[REDACTED]

[Redacted]

[Redacted]

[Redacted]

[Redacted]

[Redacted]

[Redacted]

[Redacted]

[Redacted]

[Redacted]

4 GENERAL STATISTICAL METHODS

4.1 Analysis Sets

The Intent-to-Treat (ITT) subject population includes all subjects who provide written informed consent to be enrolled into the study, met all eligibility criteria, and have a surgery initiated (i.e. anesthesia administered).

The Per Protocol (PP) population includes all subjects in the ITT Population who received the assigned treatment and had no major protocol deviations.

All primary [REDACTED] endpoint analyses will be performed on both the ITT and PP populations, with ITT considered the main analysis and PP as a sensitivity analysis; [REDACTED]

4.2 Control of Systematic Error/Bias

To reduce selection bias in this non-randomized study, each study center will be permitted to enroll subjects in only one of the treatment groups. Physicians will be selected based on device and clinical research experience and will decide which device to implant in subjects prior to study initiation at their center. This decision will be documented. All subjects meeting the eligibility criteria at the study center will be screened and enrolled, as applicable.

Imbalance between the treatment arms at baseline is a potential source of bias. To facilitate an unbiased treatment comparison, the analyses of outcomes will be based on stratification on the propensity score, as described in Section 4.3. The propensity score will be calculated from only baseline data prior to performing any analysis of endpoints, in order to avoid introducing bias from knowledge of outcome data.

4.3 Propensity Score Analysis

Analyses comparing the treatment groups will be adjusted for the propensity score. [REDACTED]

[Redacted]

[Redacted]

[Redacted]

[Redacted]

[Redacted]

[Redacted]

[Redacted]

[Redacted]

[REDACTED]

[REDACTED]

[REDACTED]

4.4 Summary Statistics

Presentations of summary statistics for continuous variables will include the count (N), mean, median, standard deviation, minimum, and maximum values. For categorical variables, the number and percentage under each category for non-missing data will be presented.

[REDACTED]

4.6 Methods for Handling Missing Data

The analyses will include only the available cases, unless specified otherwise.

Censoring times for time-to-event analyses will be at the earliest of the subject's end of study participation, death, and the time point of the analysis (e.g., for the Kaplan-Meier estimate through 12 months, the time point for the analysis is 365 days).

[REDACTED]

- [REDACTED]
- [REDACTED]
- [REDACTED]

5 ADDITIONAL DATA ANALYSES

5.1 Interim Analyses

No formal interim analysis is planned.

[REDACTED]

5.2 Justification of Pooling

In this study, the treatment difference will be estimated by pooling across propensity score strata. An analysis of the poolability will be made using logistic regression for the primary endpoint with fixed effects for treatment arm, propensity score stratum, and their interaction. The interaction will be evaluated to assess the extent of heterogeneity in the treatment difference across strata, and hence whether pooling the within-stratum treatment differences is justified. In addition, within each treatment arm, a chi-squared test will be applied to assess whether the distribution of the primary endpoint varies across the study centers. The above methods will be used in lieu of performing the protocol-specified logistic regression with effects for treatment arm and study center, since the treatment arm and center are confounded.

[REDACTED]

[REDACTED]

[REDACTED]

[REDACTED]

[REDACTED]

[REDACTED]

- [REDACTED]

[REDACTED]

[REDACTED]

[REDACTED]

[REDACTED]

[REDACTED]

[REDACTED]

[Redacted]

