**Primary Statistical Hypothesis**

The single incision sling will be non-inferior to the standard outside-in transobturator sling for the treatment of female stress urinary incontinence in safety and effectiveness at 36 months as compared to Baseline.

Statistical testing will be performed to determine if success rate of improvement in stress urinary incontinence at 36 months of single incision sling (treatment) group will be non-inferior to transobturator device (control) group. The null hypothesis is that the success rate in treatment group is less than or equal to the success rate in control group minus margin:

$$H_0: \pi_{treatment} - \pi_{control} \leq -\Delta$$

The alternative hypothesis is:

$$H_a: \pi_{treatment} - \pi_{control} > -\Delta$$

where  $\pi_{treatment}$  and  $\pi_{control}$  are the success rate of improvement in stress urinary incontinence at 36 months in treatment group and control group respectively, and  $\Delta$  is defined as the non-inferiority margin.

**Postmarket Solyx™ Study PS120093: A Prospective, Non-Randomized, Parallel Cohort, Multi-center Study of the Solyx™ Single Incision Sling System vs. the Obtryx™ II Sling System for the Treatment of Women with Stress Urinary Incontinence**

Statistical Test Method	For each of the primary endpoint and serious adverse events, non-inferiority of the single-incision sling will be evaluated using a two-sided 90% confidence interval for the treatment difference (single-incision minus transobturator). The confidence interval will be calculated based on the pooling of treatment differences across propensity score strata. All statistical analyses will be performed by the Sponsor per the Statistical Analysis Plan. [REDACTED]
--------------------------------	---

[REDACTED]	[REDACTED]
------------	------------

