## 8.2. Treatment Assignment

This post-approval study is a non-randomized, prospective, parallel cohort study across multiple centers. Subjects will be screened against the study Inclusion/Exclusion criteria and if eligible, enrolled into the study after providing Informed Consent. Approximately 140 subjects will receive the Solyx Sling System as the treatment group, and 140 subjects will receive the Obtryx II Sling System as the control group across the entire study.

To reduce selection bias in this non-randomized study, each study center will be permitted to enroll subjects in only one of the treatment groups. Physicians will be selected based on device and clinical research experience and will decide which device to implant in subjects prior to study initiation at their center. This decision will be documented. All subjects meeting the eligibility criteria at the study center will be screened and enrolled, as applicable.

. Furthermore, at study completion and final data analysis, a comparison of baseline characteristics of patients in the two groups will occur and, if necessary, statistical adjustments performed to control for baseline differences.

Should one study-wide arm reach 140 subjects prior to the other, enrollment will be capped in that arm and the other study arm will remain open to enrollment until it also reaches 140 subjects. Those study centers enrolling the device arm that have met enrollment capacity will be closed, per Sponsor discretion.

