**12.3.3. Justification of Pooling**

For each group, the analyses will be presented using pooled data across institutions. An analysis of the poolability will be made using logistic regression , with the primary endpoint as the response, fixed effects for treatment arm and propensity stratum, and a random effect for study center, to assess differences between study institutions and to justify pooling data across institutions.

[Redacted]

[Redacted]

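### Center is nested in device arm: SAP 5.2's reason for dropping the random-center model excludes only fixed center effects, its chi-squared check cannot show that center may be ignored, and whether the primary 90% CI allows for center cannot be seen

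*SAP*

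**What the plan says.** - **Assignment.** Under SAP 4.2, "each study center will be permitted to enroll subjects in only one of the treatment groups". Protocol 8.2 adds that physicians "will decide which device to implant in subjects prior to study initiation at their center". Device is therefore constant within a center.
- **Protocol 12.3.3.** Results are presented pooled over institutions. Poolability is examined by a logistic regression for the primary endpoint with "fixed effects for treatment arm and propensity stratum, and a random effect for study center".
- **SAP 5.2.** That model is replaced by two checks, used "in lieu of performing the protocol-specified logistic regression with effects for treatment arm and study center, since the treatment arm and center are confounded". One is an arm-by-stratum interaction, which says nothing about center. The other works within each arm: "a chi-squared test will be applied to assess whether the distribution of the primary endpoint varies across the study centers". The visible text gives no significance level for it and no action that follows from it.
- **Primary interval.** SAP 3.1.3 and Protocol 12.1.1.3 say: "The confidence interval will be calculated based on the pooling of treatment differences across propensity score strata for a binary endpoint". Non-inferiority is declared when the two-sided 90% CI lies wholly above -15%. SAP 4.3 is cited for the method. One sentence of it is legible, "Analyses comparing the treatment groups will be adjusted for the propensity score", and the rest is blacked out, as is most of Protocol 12.3.

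**The concern.** The SAP describes the protocol's model without saying that its center term was random. Nesting makes a fixed center effect inseparable from the device effect, but a random center effect or a center-clustered variance can still be fitted. The stated reason therefore does not justify leaving center out of the uncertainty.

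What is left is a heterogeneity test in arms of about 112 evaluable women spread over perhaps 10 to 15 centers. A non-significant result there is weak evidence that center can be ignored.

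The trial's conclusion depends on one confidence limit. If the redacted variance treats subjects as independent and outcomes correlate within center after propensity stratification, the CI is too narrow and false non-inferiority occurs more often than the nominal 5%.

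**Working it through.** **Inputs from the documents.** 140 per arm and 20% loss at 36 months (Protocol synopsis); up to 30 centers; margin 15 points; two-sided 90% CI, so one-sided 5%.

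**Assumed, because not visible.** ICC 0 to 0.10; control success 85%; 20 or 30 centers, half per arm; center sizes equal or unequal (coefficient of variation about 0.9); five strata; 5% level for the chi-squared test.

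**1. The plan's own figure.** 140 x 0.8 = 112 evaluable per arm, 224 in all, and 112/0.8 = 140. The dropout arithmetic is consistent. The 112 cannot be re-derived, since success rate and power are not visible. It fits, for example, 82.1% success with 90% power or 77.3% with 85%.

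**2. Which center effects does nesting block?** With 30 centers, one arm column and 30 center columns make 31 columns, but the arm column equals the sum of its own centers' columns. The rank is 30, so the device effect is not estimable with fixed centers. With center random, 300 simulated trials (30 centers of 8, true log odds ratio 0) all gave finite fits: mean estimate 0.006, empirical SD 0.43, median model SE 0.41.

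**3. Error by formula, equal centers, strata ignored.** Design effect DE = 1 + (m - 1) x ICC, with m = 224/K. One-sided error of a CI that ignores center = P(Z > 1.645/sqrt(DE)).
- K = 30, m = 7.47: ICC 0.01 gives DE 1.06 and error 5.5%; ICC 0.05 gives DE 1.32 and error 7.6%.
- K = 20, m = 11.2: ICC 0.01 gives DE 1.10 and error 5.9%; ICC 0.05 gives DE 1.51 and error 9.0%.

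**4. Error by simulation, stratum-pooled CI** with binomial variance; true success 85% control and 70% treatment; 20,000 trials per cell, Monte Carlo SE about 0.15-0.25 points. One-sided error, %:

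| Centers | ICC 0 | 0.01 | 0.02 | 0.05 | 0.10 |
|---|---|---|---|---|---|
| 30 equal | 5.4 | 6.1 | 6.5 | 8.0 | 10.5 |
| 20 equal | 5.9 | 6.2 | 7.0 | 9.4 | 12.7 |
| 30 unequal | 5.5 | 6.8 | 7.8 | 10.5 | 14.8 |
| 20 unequal | 5.4 | 7.1 | 8.6 | 12.6 | 17.0 |

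Part of this is the approximation itself, as the ICC 0 column shows. At ICC 0.05 with control success of 80% or 90%, the range is 7.6-12.7%. A delete-one-center jackknife with a t reference on K - 2 df gives 4.3-5.3% in all 20 cells.

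**5. The chi-squared test at ICC 0.05.** Power per arm is 19-21% with 30 centers and 23-26% with 20. Neither arm is flagged in about (1 - 0.20)^2 = 64% or (1 - 0.25)^2 = 56% of trials; simulation gives 56-65%. Expected failures per center are about 7.47 x 0.15 = 1.1 at K = 30, so the chi-squared approximation is also poor. Error of the CI that ignores center, in trials where neither arm is flagged versus all trials of the same runs: 8.1 vs 8.3% (30 equal), 9.5 vs 9.7% (20 equal), 10.3 vs 10.5% (30 unequal), 11.9 vs 12.5% (20 unequal). Passing the test barely alters the risk.

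**6. Where the decision would move.** With 85% success in both arms, SE = sqrt(2 x 0.85 x 0.15/112) = 4.77 points and the half-width is 1.645 x 4.77 = 7.85. Multiplying by sqrt(1.32) gives 9.0; by sqrt(1.51), 9.65. The observed difference needed for non-inferiority moves from about -7.1 to -6.0 (30 centers) or -5.4 (20 centers), before the t reference widens the CI slightly more.

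**The case against.** **The consequence rests on text nobody outside can read.** Error inflation arises only if the variance ignores center. That variance, and the text after SAP 5.2 and Protocol 12.3.3, is redacted. A reader might infer that the planned CI is anti-conservative, or that the plan omits center. The documents do not support either, and the point is conditional for that reason. The same holds for the absence of any visible consequence of the chi-squared test.

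**Confounded is a true word here.** Average surgeon and center differences between arms cannot be separated from the device effect by any of these models. The departure from the protocol is also disclosed. A reader might infer that restoring the protocol's model would cure the problem. It would not: it was a poolability check, not the primary analysis, and nothing here shows that it detects center variation better than the chi-squared test. The wording alone changes no result.

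**The SAP does not visibly say that a non-significant test licenses an unclustered CI.** This stands. The criticism is that the test could not support that use.

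**The size is assumed.** The ICC may be low: the protocol requires prior procedure experience and standardized procedures, and at ICC 0.01 the excess over the same CI at ICC 0 is only 0.3-1.7 points. The level of the chi-squared test is assumed too; a more liberal level would flag more trials.

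**Clustering costs power**, even when there is no correlation. This argues against imposing one particular jackknife as the only primary rule. It does not argue against reporting a clustered CI.

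**Conclusion.** The point holds in conditional form. Independent of any redaction, SAP 5.2's reason excludes fixed center effects only, and its center test is too weak at these sizes for a non-significant result to justify ignoring center.

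If the redacted variance treats subjects as independent, the one-sided error at -15% is about 5.5-7% at ICC 0.01 and 7.5-12.5% at ICC 0.05 with 20-30 centers, against 5% nominal. These figures rest on assumed ICC, success rate, strata and center sizes; more unequal or fewer centers make them worse. If the redacted text already clusters by center, only the wording of SAP 5.2 needs to change.

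A reader might extend this to the serious adverse event comparison, which the protocol synopsis describes with the same kind of CI. That was not examined, and rare events may need a different method, so no claim is made.

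**What to change.** First check the unredacted SAP 4.3 and 5.2 and Protocol 12.3 and 12.3.3 for a center-clustered variance. If there is none, amend the SAP before analysis, as SAP 5.5 allows.

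**Add to SAP 4.3:**
> A center-clustered 90% CI for the same stratum-pooled difference D will be reported beside the primary CI, whatever the result of the center test. It is D +/- t(0.95, K-2) x sqrt(V), where K is the number of centers with evaluable subjects. V is the delete-one-center jackknife variance with strata and weights held at full-sample values: the sum over arms of ((K_arm - 1)/K_arm) times the sum over that arm's centers of (D without the center - D)^2. If a deletion empties a stratum in an arm, that stratum's full-sample rate is kept. Non-inferiority will be called robust to center only if this CI also lies entirely above -15%.

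The jackknife is one example; another center-clustered variance with a small-sample reference would serve. The sponsor may instead make the clustered CI the primary one.

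**Replace the reason given in SAP 5.2 with:**
> Center is not fitted as a fixed effect because it is nested in arm. The within-arm chi-squared test is descriptive and does not decide whether to cluster. No analysis here separates average center or surgeon differences from the device effect.

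An estimated ICC should not decide either: at a true 0.05 its 5-95% range is about -0.04 to 0.15.

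**Cost.** SAP wording and a short program on data already collected; no extra subjects. The clustered CI is wider. If it were the decision rule, power would fall by roughly 1.5-6.5 points at ICC 0 and 6.5-19 points at ICC 0.05. With 30 equal centers, for example, power goes from 92.9% to 90.2% and from 89.9% to 82.6%; with 20 unequal centers, from 92.4% to 85.9% and from 86.3% to 67.7%. Part of the loss at ICC 0.05 is power that the CI ignoring center gains through excess false-positive risk.

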5.5 Changes to Planned Analyses

Any changes to the planned statistical analyses made prior to performing the analyses will be documented in an amended Statistical Analysis Plan. Changes from the planned statistical methods after performing the analyses will be documented in the clinical study report along with a reason for the deviation.

[Redacted]

[Redacted]

[Redacted]

[Redacted]

[Redacted]

[Redacted]

[Redacted]

[Redacted]

[REDACTED]

[REDACTED]

[REDACTED]

[REDACTED]

[REDACTED]

[REDACTED]

[REDACTED]

[REDACTED]

[REDACTED]

[REDACTED]

[REDACTED]

[REDACTED]

[REDACTED]

[REDACTED]

[REDACTED]

[REDACTED]
